2.3 Observational Objective(s)

Immunogenicity

- To describe the FV (dengue, YF, and Zika) serological status in the study population at baseline.

The endpoints for the observational objective are presented in [Section 9.3.1.1](#).

3 Investigators and Study Organization

This study will be conducted in Brazil. The Principal Investigators and any sub-investigators at the individual sites will be coordinated by 1 Coordinating Investigator. Details of the study centers, the Investigators at each center, and the Coordinating Investigator are provided in the “List of Investigators and Centers Involved in the Trial” document.

Safety evaluation team

An internal safety evaluation team (SET) will perform a blinded early safety analysis on safety data collected from Days 0-14 post-first injection for the first 20 subjects having received the first injection.

Independent Data Monitoring Committee

Following the SET assessment, an IDMC will review the early safety data of the first 20 subjects and will provide a recommendation on whether to continue enrollment and administration of the second dose of vaccine to the 20 already enrolled subjects ([Section 5.1.6](#)).

In addition, the IDMC will be involved in the regular review of hospitalized VCD cases, including assessment of severity. Related SAEs or deaths will be promptly reviewed by the IDMC.

Lastly, the IDMC will also be promptly notified of any significant confirmed modification of a subject’s HIV infection status, as well as if any of the criteria for interruption of the study for safety reason are met (see [Section 5.5](#)).

Others

Biostatistics, data management, monitoring, pharmacovigilance, and medical writing will be either subcontracted to a contract research organization or performed in-house by the Sponsor.

The laboratories involved in this study will be:

- Sanofi Pasteur Global Clinical Immunology (GCI), Swiftwater, Pennsylvania, USA or outsourced laboratory under the management of GCI for: dengue, YF, and Zika serological status, dengue neutralizing Ab titration, vaccine viremia testing, and virological confirmation of dengue
- Local laboratories for: screening tests (dengue IgG ELISA, hepatitis B surface antigen [HBsAg], hepatitis C virus [HCV] antibodies, hematology, and biochemistry), CD4 count, and HIV viral load assessments

The Sponsor’s Responsible Medical Officer (the Responsible Medical Officer (RMO), the person authorized to sign this protocol and any amendments on behalf of the Sponsor) is [name] [name], MSc, and Clinical Team Leader (CTL) of this study.

4 Independent Ethics Committee / Institutional Review Board

Before the investigational product can be shipped to the investigational site and before the inclusion of the first subject, this protocol, the informed consent form (ICF), subject recruitment procedures, and any other written information to be provided to subjects must be approved by, and

/ or receive favorable opinion from, the appropriate Independent Ethics Committee (IEC) or Institutional Review Board (IRB).

In accordance with Good Clinical Practice (GCP) and local regulations, each Investigator and / or the Sponsor are responsible for obtaining this approval and / or favorable opinion before the start of the study. If the protocol is subsequently amended, approval must be re-obtained for each substantial amendment. Copies of these approvals, along with information on the type, version number, and date of document, and the date of approval, must be forwarded by the Investigator to the Sponsor together with the composition of the IEC / IRB (the names and qualifications of the members attending and voting at the meetings).

The Investigator or the Sponsor will submit written summaries of the status of the study to the IEC / IRB annually, or more frequently if requested. All serious adverse events (SAEs) occurring during the study will be reported by the Investigator to the IEC / IRB, according to the IEC / IRB policy.

5 Investigational Plan

5.1 Description of the Overall Study Design and Plan

5.1.1 Study Design

This is a multi-center, observer-blind, randomized, placebo-controlled, Phase II study of the CYD dengue vaccine in 150 HIV-positive adults (18 to 50 years) in Brazil. Potential participants fulfilling all inclusion criteria, including a previous exposure to dengue according to the RDT or ELISA, will be enrolled. Subjects will receive 3 injections of either CYD dengue vaccine or placebo at 0, 6, and 12 months. The enrollment of subjects will be carried out in 2 steps, including an early safety data review (ESDR) before the second step.

Subjects HIV-positive and previously exposed to dengue according to RDT or ELISA will be randomized in a 2:1 ratio into 1 of 2 groups:

- Group 1 (N=100): subjects will receive 3 doses of CYD dengue vaccine (live, attenuated, dengue serotype 1, 2, 3, 4 virus)
- Group 2 (N=50): subjects will receive 3 doses of placebo (NaCl 0.9%)

Each subject will have her / his dengue serostatus confirmed using dengue PRNT and anti-NS1 IgG assay on the pre-injection blood sample. Subjects who are dengue-positive by RDT or ELISA at Screening Visit and dengue-negative by PRNT (sample collected before the first injection [at Visit 1] and assayed before second injection) will be considered as not previously exposed. Therefore, they will not receive any further injections and will be followed for safety until 6 months after the last dose. In addition, if they received the vaccine, provisions for timely access to medical care will be offered for 10 years after the last dose, according to IDMC prior recommendations.

All subjects are planned to be included in safety and immunogenicity analysis set. Blood samples will be taken at the Screening Visit (serology, hematology, biochemistry), and at several other time points throughout the study for baseline dengue, YF, and Zika serological status, CYD

dengue vaccine immunogenicity, dengue vaccinal viremia post-Inj 1, and HIV status monitoring assessments, depending on the time points. More details are provided in [Section 5.1.3](#).

The duration of each subject's participation in the study will be approximately 18 months.

At the end of the trial, subjects will be informed on whether they received the CYD dengue vaccine or placebo. For those who received placebo, and who have a prescription, the CYD dengue vaccine will be offered free of charge by Sanofi Pasteur through the study doctor, in accordance with the Brazilian laws and with vaccine indication in Brazil. This will be a decision between the subject and the study doctor since the vaccine offered will not be part of the trial.

5.1.2 Justification of the Study Design

CYD50 study is designed to assess the CYD dengue vaccine safety and immunogenicity in a specific population: HIV-positive persons. The fact that the study will be randomized, observer-blind and placebo-controlled will help reducing bias in the selection of subjects within this particular population and in the safety assessments. It will also help insulating the study vaccine's safety and immunogenicity assessments from some confounding factors (eg, other underlying health issues, endemicity of other flavivirus in Brazil). It is noteworthy that this study will only be enrolling HIV-positive subjects with clinically-stable condition under regular ART regimen. Also, and in agreement with the WHO position paper (WHO 2018), the study will only be enrolling subjects with a previous exposure to dengue according to RDT or dengue IgG ELISA. These criteria will both help minimize potential risks to subjects' safety and allow for a more homogeneous evaluation of the vaccine's safety and immunogenicity.

Specific inclusion and exclusion criteria have been drawn in order to evaluate the CYD dengue vaccine in this special population. Only subjects who will have had stable CD4 count (> 350 cells/mm 3) and undetectable viral load (< 50 copies/mL) for at least 1 year before consent, and who will have been on a stable ART regimen based on local HIV guidelines for at least 1 year before consent, will be included in this study [\(48\)](#). The rationale is to be able to follow stable subjects who are less likely to have complications during the study period.

CD4 count and viral load will be monitored before the first injection to ensure that participants meet the requirements set by the Brazilian Guidelines for Vaccination in HIV population [\(48\)](#). Subjects who will have had previous CD4 count < 200 cells/mm 3 (nadir) since HIV-1 diagnosis will be excluded from this study.

All subjects will be screened according to a number of parameters (see [Section 5.2.3](#)) to ensure that *i*) they are dengue seropositive and *ii*) they do not have significantly altered hematological and biochemical parameters before the first injection in case of adverse drug reaction (from either ART or CYD dengue vaccine) and/or of dengue disease. Also, due to the risk of heterologous transactivation (ie, transitory increase of viral load after vaccination), subjects that are positive for HBsAg and/or HCV antibodies will be excluded from the study. Besides, subjects' HIV infection will continue to be monitored throughout the trial according to local HIV guidelines [\(48\)](#).

More specifically, this study will allow assessing 3 distinctive features of the vaccination of HIV-positive subjects under a stable ART regimen (henceforth, the ART-population) with the CYD dengue vaccine:

How well is the CYD dengue vaccine tolerated in the ART-population. The safety of the CYD dengue vaccine in an ART-population needs to be assessed in light of the vaccine's overall safety profile. Gathering data on the same safety endpoints assessed throughout dengue studies conducted by Sanofi Pasteur will be one of the key elements in weighing the potential risks of vaccination against the potential benefits in HIV-positive individuals.

How immunogenic is the CYD dengue vaccine in the ART-population. As HIV-positive subjects have an altered immune function, the CYD dengue vaccine may not be as immunogenic as in immunocompetent persons (see [Section 1.4](#)). In order to find out whether this is also the case for the CYD dengue vaccine, this study will assess the immunogenicity of the vaccine in the ART-population 28 days after each injection.

How is the CYD dengue vaccine impacting some features of the HIV-positive subjects' immune system. Whether the CYD dengue vaccine might raise safety concerns that are specific to the ART-population has to be assessed. In this study, 2 potential safety issues will be monitored. Firstly, and as the CYD dengue vaccine is a live-attenuated virus vaccine, there is the possibility that HIV-positive subjects develop a vaccinal viremia (viremia will be assessed at D7 and D14 post-Inj 1 in all subjects). Viremia previously observed across all age groups in healthy subjects (less than 6% after the first injection, and less than 1% after subsequent injections) has not had clinical significance in the safety of subjects enrolled in earlier trials. Secondly, there is also the possibility that vaccination against dengue exerts influence in the HIV infection of some subjects ([Section 1.3.2](#)). In order to evaluate this potential risk, CYD50 will be assessing CD4 count and HIV-1 viral load 28 days after each vaccination.

It is noteworthy that only HIV-1 viral load will be assessed throughout the trial. This decision is aligned with the current local practice due to the low prevalence of the HIV-2 in Brazil, and according to the procedures included in the local guidelines for the management of HIV subjects ([48](#)).

Since cross-reactivity has been observed between FV Abs after vaccination or natural infection, previous exposure to dengue, yellow fever (YF), and Zika will be assessed at baseline using the appropriate neutralizing assays ([59-61](#)). This will allow evaluating the possible impact of recent outbreaks of Zika and YF on study participants safety and immunogenicity results ([62](#)) ([63](#)). This is especially important as the majority of Zika and YF cases are asymptomatic ([64-66](#)).

Lastly, hospitalized suspected dengue cases occurring at any time in the study will be documented. Hospitalized suspected dengue disease is defined as an acute febrile illness with diagnosis of dengue requiring hospitalization (inpatient care). In such cases, 1 unplanned blood sample (acute sample) will be collected for virological confirmation within the first 5 days after fever onset^a. A suspected hospitalized dengue case will be considered as a VCD case if there is a detection of wild-type (WT) dengue virus by non-structural protein 1 (NS1) antigen ELISA and/or wild-type dengue RT-PCR. Hospitalized VCD cases will be assessed by an IDMC for severity assessment.

^a Acute blood sample for all suspected hospitalized dengue cases should be collected within the pre-specified timeframe as described above. If this cannot be accomplished, this sample should still be obtained as soon as possible thereafter, for Independent Data Monitoring Committee (IDMC) severity assessment.

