Likewise, the safety of vaccines against JE has been assessed in a very limited number of HIV-positive subjects, all of whom were children. In 2 independent studies involving HIV-positive Thai children, no severe AEs were reported (40) (41).

It was observed that the stimulation of the immune system with vaccination may transiently increase HIV viremia, through heterologous transactivation. This usually resolves within 4 weeks (42) (43). However, this increase does not have clinical implications, as it does not correspond to virologic failure and it is not related to ART resistance. Hence, there is a possibility that vaccination against dengue is associated with this phenomenon in some subjects (42). However, in patients who received a live-attenuated oral cholera vaccine, no such activation was observed and there were no significant changes in CD4 count and HIV-1 viral load between vaccine and placebo groups (44). As per Brazil National Recommendations on vaccination of HIV-positive population, CD4 cells count will be checked before each injection (43).

Thus, and based on the scarce data on the vaccination of HIV-positive subjects against other FV (YF and JE), no safety signals are expected to occur in this descriptive study.

Placebo

No ARs are expected from placebo, except local reactions due to the injection process (eg, bruising, local pain).

All subjects

Potential risks may also include the AEs of blood sampling (ie, the discomfort from having blood taken lasting only seconds to minutes) and/or bruising.

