2.2 Secondary Objectives

Immunogenicity:

- To describe the humoral immune response to each dengue serotype at baseline and after each injection of CYD dengue vaccine in HIV-positive adults previously exposed to dengue

Safety

- To detect the CYD dengue vaccinal viremia post-Inj 1 in HIV-positive adults previously exposed to dengue
- To describe changes in CD4 count and HIV RNA viral load after each injection of CYD dengue vaccine in HIV-positive adults previously exposed to dengue

The endpoints for the secondary objectives are presented in [Section 9.2.2.1](#) and [Section 9.2.1.2](#) respectively.

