- 15) Give the subject a ruler to measure the size of any injection site reaction and a thermometer for temperature measurement, and instructions on how to use them
- 16) Remind the subject to call the study center if a serious medical event occurs
- 17) Arrange an appointment for the next visit (V02; at V01 + 7D [+ 3 day]).
- 18) Complete the relevant CRF pages for this Visit.

The visit may be postponed once if the subject is temporarily not eligible at Visit 1.

Note: The Screening Visit and Visit 1 can be simultaneous for subjects tested positive by RDT and whose tests have been performed in appropriate time windows (within 4 weeks before injection for hepatitis serology, hematology, and biochemistry; within 2 months for CD4 count and HIV viral load) as part of the subject’s routine follow-up.

Visit 2 (Inj 1+7D [+3 days]): Collection of Safety Information and Blood Sample

- 1) Check the information entered into DC1 by interviewing the subject and request information concerning any medical event, serious, or not, that may have occurred since Visit 1
- 2) Record any injection site reactions or systemic AEs and any reportable concomitant medications
- 3) Perform a physical examination and record the subject's axillary temperature (if necessary)
- 4) Obtain a blood sample (see [Section 7.1](#) for detailed instructions regarding the handling of blood samples), record the date of collection

It is important to note that, if the attempt(s) to collect blood is (are) unsuccessful, the subject should be given the opportunity for another attempt within the Visit window. If a blood sample cannot be obtained, the reason will be recorded in the blood sampling page of the CRF.

- 5) Remind the subject to call the study center if a serious medical event occurs.
- 6) Arrange an appointment for the next visit (V03; at V01 + 14D [+ 3 days]).
- 7) Complete the relevant CRF pages for this visit.

Visit 3 (Inj 1+14D [+3 days]): Collection of Safety Information and Blood Sample

- 1) Check the information entered into DC1 by interviewing the subject and request information concerning any medical event, serious, or not, that may have occurred since Visit 2
- 2) Record any AEs and any reportable concomitant medications
- 3) Perform a physical examination and record the subject's axillary temperature (if necessary)
- 4) Obtain a blood sample (see [Section 7.1](#) for detailed instructions regarding the handling of blood samples), record the date of collection

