It is important to note that, if the attempt(s) to collect blood is (are) unsuccessful, the subject should be given the opportunity for another attempt within the Visit window. If a blood sample cannot be obtained, the reason will be recorded in the blood sampling page of the CRF.

- 5) Remind the subject to call the study center if a serious medical event occurs.
- 6) Arrange an appointment for the next visit (V04; at V01 + 28D [+14 days]).
- 7) Complete the relevant CRF pages for this visit.

Visit 4 (Inj 1+28D [+14 days]): Collection of Safety Information and Blood Sample

- 1) Collect DC1 and check the information entered into it by interviewing the subject and request information concerning any medical event, serious, or not, that may have occurred since Visit 3
- 2) Record any AEs and any reportable concomitant medications
- 3) Perform a physical examination and record the subject's axillary temperature (if necessary)
- 4) Obtain a blood sample (see [Section 7.1](#) for detailed instructions regarding the handling of blood samples), record the date of collection

It is important to note that, if the attempt(s) to collect blood is (are) unsuccessful, the subject should be given the opportunity for another attempt within the Visit window. If a blood sample cannot be obtained, the reason will be recorded in the blood sampling page of the CRF.

- 5) Remind the subject to call the study center if a serious medical event occurs
- 6) Provide the subject with DC2 and remind her/him to bring it back when she/he returns for Visit 5
- 7) Arrange an appointment for the next visit (V05; at V01 + 6 months (M6) [\pm 20 days])
- 8) Complete the relevant CRF pages for this visit

Visit 5 (Inj 2 [M6; \pm 20 days]): Collection of safety information and vaccination

- 1) Collect DC2 and check the information entered into it by interviewing the subject and request information concerning any medical event, serious, or not, that may have occurred since last Visit

- 2) Record any reportable concomitant medications
- 3) Perform a physical examination and record the subject's axillary temperature before injection
- 4) Check any contraindication to vaccination
- 5) Check for confirmation of previous exposure to dengue (from PRNT laboratory results)
- 6) Perform a urine pregnancy test for all women enrolled in the study
- 7) The person in charge of injections ("vaccinator") or authorized designee contacts the IRT to obtain the assigned product to be administered

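### The first scheduled HIV-1 RNA sample after each injection is on day 28 to 42, so the trial will miss most of the transient rises its own rationale describes and can describe only persistent change

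*Protocol*

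**What the plan says.** **Risk.** Protocol section 1.3.2 explains that vaccination can raise HIV viremia for a time through heterologous transactivation. On duration it says "This usually resolves within 4 weeks". It extends this to the study vaccine: "Hence, there is a possibility that vaccination against dengue is associated with this phenomenon in some subjects". It also plays the rise down: "However, this increase does not have clinical implications, as it does not correspond to virologic failure and it is not related to ART resistance".

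**Purpose.** Section 5.1.2 cites section 1.3.2 when it raises a possible influence of vaccination on HIV infection, and continues: "In order to evaluate this potential risk, CYD50 will be assessing CD4 count and HIV-1 viral load 28 days after each vaccination". The same section excludes subjects positive for HBsAg or HCV antibodies "due to the risk of heterologous transactivation (ie, transitory increase of viral load after vaccination"). The secondary objective (section 2.2) is "To describe changes in CD4 count and HIV RNA viral load after each injection of CYD dengue vaccine", with no restriction to lasting changes. The endpoint in section 9.2.1.2 is the value at 28 days.

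**Schedule.** Section 7 places post-injection HIV viral load at Visits 4, 6 and 8 only. Section 5.1.4 introduces the first of these as "Visit 4 (Inj 1+28D [+14 days"]), and Visits 6 and 8 have the same one-sided window. The repeat test comes 4 weeks after the first (section 5.5). Earlier blood draws exist after injection 1: "Visit 2 (Inj 1+7D [+3 days]): Collection of Safety Information and Blood Sample", and Visit 3 on day 14. Protocol Table 5.1 uses them for dengue vaccinal viremia only. After injections 2 and 3, days 7 and 14 are phone calls.

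**Analysis.** Protocol section 12.1.2.2 promises a summary of HIV-1 RNA over time. SAP sections 4.4.1.5.10 and 5.1.2.2 and SAP Table 5.1 give only yes/no indicators: below 50 copies/mL before injection and above 1000 after, with a confirmed version.

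**The concern.** Transactivation is the only mechanism that section 1.3.2 gives for a viral-load rise after vaccination, and the protocol expects it usually to be over by the time the first sample is due. A near-zero count at day 28 is therefore what the protocol's own account predicts, whether or not transactivation occurs with this vaccine. The results are intended for the Risk Management Plan (section 1.4), where a reader could easily take such a count as showing no effect on viral load. No section reconciles the 28-day timing with the 4-week resolution or says that only lasting changes are sought.

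The SAP flag narrows the view further. A rise that is still partly present at day 28, at 50 to 1000 copies/mL, is recorded as No. The over-time summary that would show it is in the protocol but not among the SAP's methods.

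**Working it through.** **1. Timing (protocol sections 5.1.4 and 5.5).** The first sample falls on day 28 to 28 + 14 = 42 after each injection. The repeat falls on about day 28 + 28 = 56 to 42 + 28 = 70. A rise that resolves within 28 days is over at or before the earliest permitted sample.

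**2. The plan's own figure (section 12.5).** Chance of at least one event at 3% incidence among 100 vaccinees: 1 − 0.97^100 = 0.9524. The stated 95% reproduces.

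**3. Effect of late sampling.** Let p be the true incidence of a rise after one injection, and f the share of rises still elevated when sampled. The documents give no f. Reading usually as more than half resolved puts f below 0.5, so 0.5 to 0.05 is taken as an assumed range. The chance of at least one observed case is 1 − (1 − p·f)^100. The incidence needed for a 95% chance is (1 − 0.05^(1/100))/f = 0.0295/f.

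| f (assumed) | chance at p = 3% | incidence needed for 95% |
|---|---|---|
| 1 | 95.2% | 3.0% |
| 0.5 | 77.9% | 5.9% |
| 0.25 | 52.9% | 11.8% |
| 0.10 | 26.0% | 29.5% |
| 0.05 | 13.9% | 59.0% |

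For the SAP flag, f counts only rises still above 1000 copies/mL, so it is no larger than the share still detectable. The table is for one injection. If the same 3% applied independently at all three injections in all 100 subjects, f = 0.10 would give 1 − 0.997^300 = 59.4%.

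**4. The flag, with assumed kinetics.** None of the following inputs is in the documents, and the result concerns only the above-1000 flag. Take a peak of 5,000 copies/mL on day 7, 21 days before the earliest sample.

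- Half-life 5 days: 5000/2^(21/5) = 5000/18.4 = 272 copies/mL on day 28.
- Half-life 2 days: 5000/2^(21/2) = 5000/1448 = 3.5 copies/mL.
- Day-7 peak needed to reach 1000 on day 28 with a 5-day half-life: 1000 × 18.4 = about 18,400 copies/mL.

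The value of 272 is more than five times the 50 copies/mL limit. It would appear in a summary of viral load over time, but the flag records No.

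**5. Hold signal (section 5.5).** The viral-load signal needs confirmed rises in 20% of subjects, 0.20 × 150 = 30. Confirmation requires the value or trend to be present about 2 months after injection, so this signal responds only to persistent rises.

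**The case against.** The best defence is that persistence is the right target. Section 1.3.2 calls the transient rise clinically unimportant, the repeat test exists to confirm real deterioration, and the endpoint is expressly the 28-day value. Sampling after a harmless rise has subsided avoids false signals. The risk in section 5.1.2 is also broader than transactivation: it is any influence on the HIV infection, assessed by CD4 count as well as viral load.

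This is a coherent design position, but the protocol does not state it. Section 5.1.2 sends the reader to section 1.3.2 for the risk, and treats the temporary rise as a reason to exclude subjects with hepatitis markers.

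Other points stand in part:

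- The 4-week figure comes from cited sources, one of which, by its title, studied a recall antigen. Section 1.3.2 also reports no activation after a live oral cholera vaccine. The time course in this suppressed population is therefore unknown, and so is whether day 7 or 14 would catch a peak.
- No section says that a null day-28 result will be reported as no effect. The risk is one of interpretation.
- Early draws exist only after injection 1, so they cannot supply early data for all three injections.

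A reader might go further and infer that the trial cannot describe the HIV-1 RNA change it set out to evaluate. The documents do not support that. Usually leaves some rises visible at day 28 to 42, so detection is reduced, not zero. Persistent rises can be compared with placebo, the 28-day endpoint can be estimated, and the argument does not touch the CD4 results.

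**Conclusion.** The concern holds in limited form. The schedule will miss most transient HIV-1 RNA rises and describes only changes that persist to day 28 to 42. A low day-28 count does not show that transactivation is absent. That conclusion rests on the protocol's own 4-week statement and its visit windows.

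The size depends on f, which is assumed. At 3% incidence after one injection, the chance of seeing any case falls from 95.2% to 77.9% at f = 0.5 and to 26.0% at f = 0.10. The 95.2% for early sampling assumes that nearly all rises would be present at day 7 or 14, which the documents do not show. The figure of about 18,400 copies/mL should not be read as the peak needed for detection: it follows from an assumed half-life and peak day, and applies only to the above-1000 flag.

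This is a mismatch between rationale and measurement, made worse by the SAP's reliance on the flag. It does not invalidate the endpoint.

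**What to change.** **Preferred.** Add an HIV-1 RNA tube to the existing Visit 2 (day 7) and Visit 3 (day 14) draws in protocol Table 5.1, the Table of Study Procedures and SAP Table 3.1. Summarise the values by arm as a descriptive secondary result. State how they relate to the SAE and hold criteria, which are defined on the 28-day value. This covers injection 1 only; injections 2 and 3 would need new visits.

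Cost: no new visit or venepuncture, up to 10 mL more blood at each draw (4 mL becomes up to 14 mL), and 150 × 2 = 300 local viral-load assays.

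**Otherwise**, or if injection 1 sampling is already over: amend section 5.1.2, the secondary endpoint and the study-report conclusion to say that day 28 to 42 values describe persistent change only and do not exclude transient rises. This costs wording and a more modest claim.

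**In either case**, carry the protocol's summary of viral load over time into SAP section 5.1.2.2 and SAP Table 5.1, by arm, showing values of 50 to 1000 copies/mL separately. This needs one further table and no new data.
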